3. STUDY OUTCOMES

3a. Primary outcomes

Aim 2: Stepped-wedge randomized controlled trial (RCT)

The primary outcome for this study is **adolescent retention in HIV care**, defined as:

 Return for 1st follow-up visit after first enrollment visit OR return for follow-up visit after a 're-engagement visit' among adolescents who had previously been lost to follow-up (LTFU) • Retention in care for ANY follow-up visit within 3 months among adolescents currently enrolled in HIV care (which can be referred to as "actively enrolled")

Description:

First follow-up visit after enrollment visit: The number and proportion of adolescents who return to clinic within 3 months of an enrollment visit

Follow-up visit after re-engagement in care among LTFU adolescents: Lost to follow-up is defined as no clinic record for at least 3 months, and no record of death or transfer to another facility. Among adolescents who return to clinic after LTFU, we will collect the number and proportion of adolescents who return for a subsequent visit within 3 months.

Return for follow-up among those currently enrolled in care: To evaluate whether the SPEED intervention may result in better adherence to visit schedule among adolescents currently enrolled in HIV care (i.e. not newly enrolled or previously LTFU), we will also measure return for any follow-up visit within 3 and 6 months.

3b. Secondary outcomes:

Aim 1: Pilot testing of case scripts and establishment of competency

- Final case scripts
- Numeric scores on HCW checklist
- Proportion of HCWs with pass/fail scores
- Numeric scores on actor feedback checklists
- Numeric scores on HCW satisfaction survey
- Numeric scores on HCW self-rated competency survey

Aim 2: Stepped-wedge randomized controlled trial

In addition to the primary outcomes, the RCT will have several secondary outcomes, summarized in in Table 1:

Analyses of *process outcomes* to understand intervention mechanism will include:

- Pre/post-measures of HCW and patient satisfaction
- Pre/post-measures of HCW competency scores
- Associations between HCW competency scores and care outcomes
- Associations between HCW competency scores and adolescent satisfaction outcomes

• Exit interviews in a purposeful sample of HCW participants at the end of the trial

Table 1. Summary of process outcomes, exploratory outcomes, and indicators in Aim2 RCT

Process Outcomes	Indicator	Source
HCW competency	Mean HCW scores per clinic	Faculty graded scores
		Exit interviews
HCW satisfaction	Mean HCW score per clinic	HCW survey
Adolescent patient satisfaction	Mean adolescent score per clinic	Tablet-based questionnaire
Clinical/Exploratory Outcomes		
Adherence	Refills within 1 week of scheduled return visit	Clinic/pharmacy records
Viral suppression	Viral load (VL) <1000 copies per ml and a second analysis using VL <400 copies/ml	Clinic records
Linkage to APS services	STI/TB screening, Contraception uptake, mental health referral	Clinic records
AIDS defining illness	Diagnosis of at least one AIDS defining illness per national guidelines	Clinic record
Mortality	Death during follow up	Clinic records

Aim 3: Cost Effectiveness Analysis (CEA) and Cost Utility Analysis (CUA)

This aim will assess the following measures:

- SPEED intervention costs
- Cost per additional HIV-infected adolescent retained in care
- Cost per additional life year saved and disability-adjusted life year (DALY) averted. This estimate is the gold standard in health economics. This analysis will be performed once an adequate mathematical model of adolescent DALYs is developed.

Additional exploratory outcomes

- Cost per additional HIV-infected adolescent with ≥80% adherence
- Cost per additional HIV-infected adolescent virally suppressed
- Cost per additional HIV-infected adolescent linked to APS services

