part of the intervention. The study team will meet with clinic leadership and managers
first to gain access to providers. A study staff member will then approach those providers
to invite them to learn more about the study.

Within participating clinics, all clinical providers who have contact with adolescent clients will be approached for participation. Eligible providers at that facility will give informed consent (see Section 13). Eligible providers at that facility will give informed consent. We anticipate an average of 10 HCWs per site, depending on clinic size.

 Adolescents attending clinics: A clinical staff member will be instructed by our Study Team to refer consecutively, all adolescents seeking HIV care on a given day, to the Study Team member. This Team member will be at each clinic to invite adolescents to complete an anonymous, tablet-based survey to assess satisfaction with their counseling or treatment encounter. We will track numbers of adolescents referred compared to total adolescent patients, and reasons for not referring to identify any differences in referrals by time of day or day of week.

We expect to enroll at least 5 adolescents per clinic per time period and up to 20, depending on clinic volume (20 adolescents X 5 time periods X 24 clinics = up to 2,400). A Study Team member will be at each clinic for 1-3 days for recruitment.

Retention strategies for HCWs and adolescents: While the intervention targets health facilities, we will track individual providers to assess retention in service provision at clinical intervention sites, using a facility survey to monitor staff turnover. In addition, provider names and phone numbers will be recorded, and we will assess the provider's continued employment at the sites, as well as any cross-over to other study sites, at each measurement time point. Adolescent surveys will be cross-sectional at each time point. Accordingly, there is no need for a retention strategy for this group.

Cost Effectiveness Analysis and Cost Utility Analysis (CUA)

No participants will be recruited specifically for this analysis. Questions on direct and indirect costs, as well as clinic and hospital visits, to the adolescents will be included in the adolescent satisfaction survey (Appendices). Other cost data will be drawn from program data, the literature, and our prior studies.

5f. Randomization procedures

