8. STUDY SCHEDULE

In this trial, there will be 4 waves of 6 clinics per wave, and 5 measurement periods, including baseline (Table 3). Total duration of the trial is approximately 3 years. Each wave will be rolled out approximately every nine months. Data pulls will occur 15 months after the HCW training, to ensure that all clients who present within the exposure time period have a full 6 months to return for care.

	Introduction of Intervention									
Clinic clusters	Baseline	Month 1	Month 10	Month 19	Month 28					
Wave 1: Sites 1-6	0	Х	Х	Х	Х					
Wave 2: Sites 7-12	0	0	Х	Х	Х					
Wave 3: Sites 13-18	0	0	0	Х	Х					
Wave 4: Sites 19-24	0	0	0	0	Х					

An overview of the anticipated overall study schedule for one wave is shown in Table 4, following page. The study will be conducted over five years. During year one, we anticipate script development, recruiting and training SPs, developing measurement checklists, and piloting initial encounters at Kenyatta National Hospital. During year two, we will recruit and randomize study sites, and begin implementation of the intervention. The intervention will be rolled out in waves, completing measurement and intervention cycles during year 4. Year 5 will be dedicated to statistical outcome analyses, cost effectiveness analyses and modeling, and dissemination of study findings both locally and internationally.

SPEED Protocol Protocol # Version 7.0 May 11 2020

Table 4. Overview of SPEED Study 2015 - 2020

	Y1		Y2			Y3			Y4				Y5							
	Q1	Q2	Q3	Q4																
Study Planning		1		I	1		I													
Protocol development																				
IRB Submissions																				
Implementation	r			1	1	ī	r	Ū	ī											
Site selection																				
Actor Training																				
Pilot phase																				
Consents & Randomization																				
Baseline OR EMR data pull					х				х				х				х	х		
Wave 1																				
Training																				
Exposure time & data pull (X)									Х											
Wave 2					Х															
Training																				
Exposure time & data pull (X)												Х								
Wave 3					Х															
Training																				
Exposure time & data pull (X)															Х					
Wave 4					Х															
Training																				
Exposure time & data pull (X)																		Х		
Post-trial data pull																			Х	
Analysis																				
Data Analysis																				
Dissemination	1	1		1			1													

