using an Excel spreadsheet. These data will be collected at baseline assessment. Cost data will be updated, as needed, at the end of the trial.

Data sources from adolescents

- Clinic records: De-identified adolescent clinic records from the EMR system will extracted at baseline, and at the end of each wave to assess primary and clinical outcomes, according to our data use agreement with NASCOP. Data from each pull will capture all records until the previous data pull. Examples of data will be visit dates, enrollment status (newly enrolled or existing), date of birth/age, sex, viral load and CD4 counts, pharmacy records, and referrals to family planning/TB/STI services.
- Adolescent satisfaction, cost, and sexual behavior surveys: Anonymous post-visit surveys will be conducted with adolescents using electronic tablets. These surveys will be conducted at baseline and at the end of each wave in all sites. Information will include basic demographics (age, schooling), type of service received/reason for visit, satisfaction with services received, perception of judgment by the health HCWs, and intent to return for services. Questions will also ask about direct and indirect costs associated with seeking care that the facility (e.g. cost of transportation, lost wages). The last section of the survey will be self-administered and ask questions about sexual behavior and sexual partners using electronic tablets. These surveys will be conducted at immediately after the satisfaction and costs surveys.

Data Management Responsibilities

A dedicated data team will be responsible for the entry, management, and monitoring of study data, in accordance with standard operating procedures. The Nairobi data team will communicate frequently with the Seattle-based statistical team for reporting, data cleaning, study monitoring, and interim analyses. Study data uploaded to the secure study cloud server using Open Data Kit (ODK). Open Data Kit is a secure, web-based application designed by UW faculty to support data capture for research studies. The software provides 1) an intuitive interface for validated data entry; 2) automated export procedures for seamless data downloads; and 3) procedures for importing data from external sources.

Data Capture and Storage Methods

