A CONSORT diagram, adapted for a stepped-wedge design [34] will be used to show the number of HCW-participants within clusters and flow of randomized stepped wedge clusters though the five time periods. We will report the number of clinics selected for inclusion, assignment to intervention or control at each time period, and the number of HCWs trained at each facility. We will report number of excluded clusters and any reasons for exclusion. No replacement will be used. Facility-specific information – adolescent patient volume, number of HCWs and presence of any adolescent-specific service (peer groups, clinics etc.) prior to the intervention – will be grouped by clinic and recorded. Baseline values of primary and process outcomes, and socio-demographic characteristics of adolescents and HCWs will be presented in a descriptive table.

We will use generalized linear mixed models (GLMM), which are more efficient than paired ttests and linear mixed models (LMMs) in the analysis of cluster RCTs when the size of clusters is unequal [32] to compare the probability of an adolescent returning to clinic after enrollment visit OR second visit after >3 months LTFU between the intervention and control periods [35]. To estimate the effect of the intervention (*Xij*) on the individual level, we will use a GLMM model with a Poisson distribution and robust standard errors, allowing for random effects for clusters (*ui*) and fixed effects for time (*j*). This approach models individual level outcomes, adjusts for temporal trends and accounts for correlation of outcomes within a cluster (clinic). We will estimate adjusted risk ratios (ARR), adjusted risk differences (ARDs) and 95% confidence intervals at the 5% significance level (two-sided). Adjusted risk ratios will be estimated for secondary outcomes: initiating and adherent to ART (≥80% in the dosing period by pharmacy records), 12-month retention in care; viral suppression (<100 copies/ml, <1000 copies/ml), and referred for ancillary services (family planning and TB screening). Models will be adjusted for facility type, patient volume, and exposure to prior adolescent health interventions (c).

The equation for a generic model is: $Y_{ijk} = \beta_0 + \beta j_{time} + \beta_{effect} X_{ij} + \beta c X ij$, $ui + \varepsilon ij$

- Analyses of process outcomes to understand intervention mechanisms will include:
 - Mean HCW competency (passing score proportion per clinic) before and after the intervention

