 - Association between mean HCW competency scores per facility and adolescent satisfaction scores
 - Associations between mean adolescent satisfaction scores and 1) retention in care (binary), 2) referral to APS services (binary), 3) ART adherence (binary or mean percent), and 4) viral suppression (binary) comparing the exposed and unexposed periods.
- Evaluation of temporal trends: Temporal trends that change over time (e.g. introduction of new HIV treatment guidelines, COVID-19) and potentially impact study outcomes can lead to a biased effect estimate in a stepped-wedge trial design [34]. To assess this possibility, we will repeat the primary analyses including an interaction term between a time indicator (e.g. coded as 'pre' versus 'post' policy/program change) and the variable for the main effect. A p-value for the interaction <0.1 will be evidence of interaction. We will report these results in a separate table showing any differences in intervention effect by this temporal change.

- Lag effects of SPEED intervention: Because the effect of the intervention may not be immediate or it may diminish over time, we will evaluate these possibilities in two ways. HCWs may take time to put skills they learned in the training into practice. In addition, trained HCWs may decrease or stop using these new skills. Intervention lag will be modeled by re-coding the first month after the intervention as a control period, as recommended by Davey *et al.* [34]. We will model the reduction of the intervention effect over time by using a fractional term for the coefficient of primary effect estimate, which will have a value of 1 (assumes 100% exposure) and get smaller at each time step (e.g. 75%, 50%, 25%).
- Qualitative analysis of exit interviews: Qualitative data from the HCW exit interviews will be coded in Atlas.ti. Data will be analyzed by two reviewers using thematic analysis according to the interview guide. These results will be utilized to complement results from the structured HCW satisfaction surveys.

Cost-effectiveness Analysis (CEA) and Cost Utility Analysis (CUA)

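### Adolescent satisfaction is given only a pre/post measure and no model with time effects, so a literal pre/post contrast would mix calendar trend with the training effect

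*Combined protocol and SAP*

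**What the plan says.** - **Status of the outcome.** The protocol summary lists satisfaction of adolescents and health care workers (HCWs) among the secondary outcomes. Table 1 in section 3b classes adolescent satisfaction as a process outcome, with the indicator "Mean adolescent score per clinic".
- **Analysis named.** Section 3b, under the process analyses for Aim 2, gives "Pre/post-measures of HCW and patient satisfaction". It does not say which rounds count as pre and post, or what model or test applies.
- **Data.** Section 11 says of the adolescent surveys: "These surveys will be conducted at baseline and at the end of each wave in all sites". Section 5e adds: "Adolescent surveys will be cross-sectional at each time point".
- **Schedule.** Section 8: "In this trial, there will be 4 waves of 6 clinics per wave, and 5 measurement periods, including baseline". It continues: "Each wave will be rolled out approximately every nine months".
- **Time-adjusted model.** Section 12c specifies a mixed model with clinic random effects and fixed time effects for return after an enrolment or re-engagement visit. It then says "Adjusted risk ratios will be estimated for secondary outcomes: initiating and adherent to ART", followed by 12-month retention, viral suppression and referral. Satisfaction is not in that list. A generic equation with a time term is printed without saying which outcomes it covers.
- **Process outcomes in 12c.** Competency is to be described before and after the intervention. Adolescent satisfaction appears only in associations: with HCW competency, and in the item that begins "Associations between mean adolescent satisfaction scores and 1) retention in care (binary". No time term is named for either.
- **Temporal trends.** Section 12c warns that changes over time, such as new treatment guidelines or COVID-19, can bias a stepped-wedge estimate. The check it sets out repeats only the primary analyses.

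**The concern.** Clinics cross over in one direction only, so within a clinic every post round comes after every pre round. A before/after difference therefore contains the training effect plus whatever happened to satisfaction everywhere over the same months. The last round has no untrained clinic, so a shift confined to that round falls entirely on the exposed side.

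The process outcomes are there to explain mechanism. If satisfaction rose in all clinics for other reasons, an analyst following section 3b literally could present the rise as evidence that the training works through patient experience. The association analyses have the same weakness: two quantities that both drift with calendar time can look linked when they are not.

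**Working it through.** **The plan's own figure.** Section 5e gives the survey total as 20 adolescents × 5 time periods × 24 clinics = 2,400, which reproduces. The plan states no pre/post gap and no power for satisfaction.

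**Step 1: the gap in calendar time.** Inputs are the 0/X layout of Table 3 and nine-month spacing (section 8). Rounds are numbered 0 to 4, at months 0, 9, 18, 27 and 36.

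| Wave | Control rounds | Exposed rounds | Mean control | Mean exposed | Gap (steps) |
|---|---|---|---|---|---|
| 1 | 0 | 1–4 | 0 | 2.5 | 2.5 |
| 2 | 0–1 | 2–4 | 0.5 | 3 | 2.5 |
| 3 | 0–2 | 3–4 | 1 | 3.5 | 2.5 |
| 4 | 0–3 | 4 | 1.5 | 4 | 2.5 |

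- Within clinic: 2.5 × 9 = 22.5 months in every wave.
- Pooled, control: (0 + 1 + 3 + 6)/10 = step 1.0.
- Pooled, exposed: (10 + 9 + 7 + 4)/10 = step 3.0.
- Pooled gap: 2.0 × 9 = 18 months.

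Other readings:
- Surveys at months 0, 10, 19, 28 and 37: 18.4 pooled, 22.8 to 23.5 within clinic.
- Table 3 column months (0, 1, 10, 19, 28) taken as survey dates: 14.8 pooled, 14.5 to 20.5 within clinic.
- Last pre round against first post round at nine-month spacing: 9 months.

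A shorter gap, 1 month for wave 1, arises only if the column months are survey dates and adjacent rounds are compared. That does not fit section 11, which puts surveys at the end of each wave. The gap is positive on every reading.

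**Step 2: what a trend does.** Expected unadjusted contrast = training effect + (drift per month × gap). With fixed round effects the gap term is zero.

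**Step 3: illustration.** The documents give no drift or intraclass correlation (ICC) for satisfaction, so both are assumed: a linear drift of 0.2 SD over 36 months, no training effect, a two-sided 5% test, and a clinic random intercept with or without round effects. The sample n per clinic-round is 5 or 20 (section 5e).

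| ICC | n | Effective gap (months) | False effect (SD) | SE, no round effects | Rejects | SE, round effects | SE ratio |
|---|---|---|---|---|---|---|---|
| 0 | 5 | 18.0 | 0.100 | 0.0816 | 23.2% | 0.1155 | 1.41 |
| 0 | 20 | 18.0 | 0.100 | 0.0408 | 68.8% | 0.0577 | 1.41 |
| 0.05 | 5 | 20.31 | 0.113 | 0.0845 | 26.6% | 0.1280 | 1.51 |
| 0.05 | 20 | 21.64 | 0.120 | 0.0436 | 78.7% | 0.0691 | 1.58 |
| 0.2 | 5 | 21.75 | 0.121 | 0.0803 | 32.5% | 0.1276 | 1.59 |
| 0.2 | 20 | 22.29 | 0.124 | 0.0406 | 86.2% | 0.0658 | 1.62 |

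Example, ICC 0.05 and n = 20: 0.2/36 × 21.64 = 0.120 SD; 0.120/0.0436 = 2.76 standard errors.

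**Step 4: a shift in the last round only.** The last round supplies 24 of the 60 exposed clinic-rounds and none of the 60 control ones, so the shift enters the pooled difference at 24/60 = 40% of its size. With round effects it enters at zero.

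**The case against.** The strongest reply is that nothing commits the trial to an unadjusted comparison. The wording in section 3b names a measure, not a model. Section 2b describes retention in similar before/after terms, and 12c then models it with time effects. The generic equation also has a time term. This stands. A reader might infer that any calendar trend will be reported as a training effect; the documents do not support that. They leave the analysis open. But for retention 12c closes the gap that 3b leaves, and for satisfaction it does not.

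Absence from the adjusted-risk-ratio list is weak evidence by itself. The list also omits mortality and AIDS-defining illness, and a mean score does not lend itself to a risk ratio. That too stands, though for the same reason the sentence cannot be stretched to cover satisfaction.

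A reader might also infer that the design leaves satisfaction unprotected. It does not: surveys run in all sites at every round, so the design protects satisfaction as well as retention, and only the analysis wording is missing. Nor should the concurrent comparison be overstated. Untrained clinics are present in four rounds, but trained and untrained clinics coexist in only three.

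Finally, the rejection rates rest on an assumed linear drift and a test that the plan does not state. They are illustrative only.

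**Conclusion.** The point holds as a gap in specification with a predictable direction of risk. The plan names only a pre/post measure for the effect of training on adolescent satisfaction and assigns that outcome no model with time effects. Taken literally, the contrast compares rounds 18 months apart (pooled) or 22.5 months apart (within clinic), assuming nine-month spacing and all rounds averaged; the other readings consistent with end-of-wave surveys or the Table 3 months span 9 to 23.5 months. The bias equals the drift over that gap, and its size and sign are unknown.

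The stakes are limited to a secondary, mechanistic outcome. The return-to-clinic analysis already has fixed time effects, so the main effectiveness conclusion does not depend on this.

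**What to change.** - **Adolescent satisfaction.** Replace the pre/post wording with a mixed model on individual scores from all 24 clinics and 5 rounds: clinic random effect, fixed effect for each round, exposure indicator, and a linear or ordinal outcome as the scale requires.
- **Association models.** Add round effects and a clinic random effect to the models linking satisfaction with care outcomes. Do not use fixed clinic effects where the faculty-graded competency score is a predictor: section 11 has it graded once, at training, so a clinic's mean score would be absorbed and its association could not be estimated.
- **HCW satisfaction.** Report the pre/post comparison as descriptive. Section 11 collects it only at baseline and in the training, so there is no concurrent untrained comparison.

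The cost is SAP wording and precision; no new data are needed. The standard error rises by a factor of about 1.4 to 1.6 (for example from 0.044 to 0.069 SD at 20 surveys per clinic-round and an assumed ICC of 0.05), so the interval will be wider.
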